## 11. Study Framework

This is a prospective observational study of RDV. It's objective is to evaluate RDV in the context of its use initially under EAMS and then under standard guidelines in the UK. Hypotheses will test for superiority. Outcomes are defined to allow direct comparisons with the clinical trial outcomes defined in ACTT-1 and SOLIDARITY. The scope of this study to measure isolated efficacy of RDV is clearly limited by the observational nature of the data; but the evaluation of outcomes will give a pragmatic summary of the current prognosis for this population of severe COVID with and without RDV.

## 12. Confidence Intervals, p-values and Multiplicity

Confidence intervals will be reported for all point estimates at the 95% level. Baseline summaries will be presented to 1 decimal place whilst all other values will be reported to 2 decimal places, or 1 significant figure if it would round to zero at 2 decimal places, and all p-values will be reported to 3 decimal places. There are no planned adjustments for multiplicity.

## 13. Timing and objectives of interim and final analyses

### 13.1. Progress reports

No interim/progress reports are planned. At the time of writing, RDV is no longer the subject of an EAMS objective, and the study's aim is simply to evaluate its use thus far.

### 13.2. Final analysis

Data collection will continue until the end of November 2020, in order to include patients from both the 1st and 2nd wave of UK COVID infections. It is then envisaged that the statistical analysis will be completed by the end of January 2021.

## 14. Disposition of Participants

A CONSORT style flow-chart will summarise the flow of patients through analysis stages: the number of patients with an admission CRF recorded by CCP-UK; the number of patients included and excluded due to inclusion/exclusion criteria; of those included – the numbers that received RDV; numbers of non-RDV patients; the total number of RDV and non-RDV patients included in the matched analysis; numbers of RDV patients and matched controls included in the primary outcome analysis.

## 15. Treatments received

This study did not define an *a priori* protocol for clinicians treating COVID-19 patients. Reporting of protocol deviations will be limited to a count of patients that did not receive RDV according to guidelines, and to an assessment of missingness in the derivation of the primary and secondary outcomes. Treatments received are recorded in the Medication section of the Outcome CRF. These will be summarised in the matched cohort, split by treatment group. If there is evidence of imbalance between groups with respect to certain treatments, we will consider whether to adjust for this in the final analysis.

## 16. Unblinding

Not applicable.

## 17. Efficacy Evaluations

### 17.1. Demographics and other baseline characteristics

Descriptive statistics will be used to describe demographics and other baseline characteristics, including pre-existing comorbidities for (a) the full analysis cohort, (b) the matched cohort, split by treatment group.

Categorical data will be summarised by numbers and percentages. Counts for missing values will be also tabulated but missing values will not be considered in the percentages. Continuous data will be summarised by mean, standard deviation, median, lower quartile, upper quartile, minimum and maximum. Variables to be included are as follows:

- Gender (Male/Female)
- Age, reported as a continuous variable (years) and also by age-group (18-30, ..., 71-80, 81+)
- Broad ethnicity (White / Black / Asian / Other)

- Non-white ethnic origins (Arab/Black/East Asian/South Asian/West Asian/Latin American/Aboriginal/First Nations/Other)
- Clinically extremely vulnerable status (None / Cancer / Severe respiratory condition / Immunosuppression therapy / Other)
- Comorbidities (Diabetes, Hypertension, Obesity, Chronic Cardiac disease, CPD, Asthma, Other)
- Where COVID was acquired (Community / Hospital)
- Number of days since onset of symptoms
- Admitted to HDU/ICU

## 17.2. Analysis of Outcomes

### 17.2.1. Primary Outcome

The percentage of patients that died by the end of day 14 will be presented for each group. Risk of death will be modelled using logistic regressionf,10, with treatment group fitted as a covariate, and ideally adjusting for the key confounders: age, sex, and number of comorbidities at baseline. The odds-ratio comparing RDV with controls, estimated from the model, will be presented together with a 95% CI and a p-value.

Note on adjustment for confounders: the number of covariates that may be added to the model depends on the number of deaths recorded (rule of thumb, 10 events per covariate fitted). Clinical trials data indicate that 14-day mortality for RDV in this type of patient may be around 3.1%, meaning that if we include 500 RDV-treated patients, we might expect 16 deaths from that group. Under the assumption that the risk of death is not lower in the control group, this suggests at least 32 deaths (under 1:1 matching), and so we project that there will be sufficient power to enable adjustment for 3 confounders given the higher expected matching ratio.

---

f Stuart (2010) recommends that in the analysis of cohorts matched using propensity scoring, it is more common to simply pool all the matches into matched treated and control groups and run analyses using the groups as a whole, rather than using the individual matched pairs.

## 17.2.2. Secondary Outcomes

### 17.2.2.1. Time to recovery

Recovery is defined as discharge from hospital or continued hospitalisation with no on-going health-care needs related to COVID-19. For patients that recover, a time-to-event is defined as the number of days from baseline to discharge, or from baseline to cessation of COVID-19 related health-care (whichever occurs first). All other patients are censored at last available follow-up or 28 days (whichever occurs first). All deaths before 28 days (with no prior recovery) will be censored at day 28g. A Cox proportional hazards model will be used to model time-to-recovery, fitting treatment as a covariate, and adjusting for the key confounders: age, sex, and number of comorbidities at baseline. The hazard ratio comparing RDV with controls estimated from the model will be presented together with a 95% CI and a p-value. Kaplan-Meier graphs comparing recovery by treatment group will be presented – for the full matched cohort; and for key age-groups: <50, 50-59, 60-69, 70-79, ≥80 years.

### 17.2.2.2. 28-day mortality

The same methodology as used in 17.2.1 above will be applied here for risk of death at day 28.

### 17.2.2.3. Time-to-death

We restrict this analysis to deaths within 28 days of baseline. Any patient alive at the end of the study period will be censored at 28 days. Any patient lost to follow-up prior to 28 days will be censored at their last known follow-up. This outcome will be analysed as a time-to-event using the methodology described in 17.2.2.1 above.

### 17.2.2.4. Clinical status at day 15

Clinical status is defined as an 8-point ordinal score with the following categories: (1) Not hospitalised, and not limited physically; (2) Not hospitalised, but limited physically and/or requiring supplementary oxygen; (3) Hospitalised but medically OK; (4) Hospitalised, not requiring supplementary oxygen, but needs on-going COVID related care; (5) Hospitalised and requiring supplementary oxygen; (6) Hospitalised and requiring non-invasive ventilation; (7) Hospitalised and requiring mechanical ventilation or ECMO; (8) Dead. See Appendix A1.1 below for a definition of how this outcome is derived. Where day 15 CRFs are unavailable, we will look at all available adjacent CRFs to estimate a

---

g We have used the same definition for this outcome as was used in the ACTT-1 trial.

most likely clinical status. In cases where there is ambiguity over likely clinical status, and independent statistical reviewer, blind to all but the clinical status CRF data, will adjudicate likely status. If it is not possible to estimate the outcome, the outcome will be treated as missing.

The outcome will be analysed using a proportional odds model with treatment arm and disease severity as covariates, and adjusting for key confounders: age, sex, and number of comorbidities at baseline. The treatment odds ratio estimated from the model will be presented along with a 95% CI and a p-value.

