## 8.8. Sequence and duration of study periods

All patients are followed up until discharge, death, or 28 days post baseline – whichever occurs first.

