## 8.9. Schedule of assessments

Data are collected on patients per the CCP-UK Tier Zero schedule and: on each day of RDV dosing, on day 14 after RDV initiation, then on death, discharge or day 28 post hospitalisation, depending which is soonest.

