#### 17.2.2.6. Time-to-first ventilation

The DAILY CRF will be used to define, where possible, date of first use of ventilation. Any patient not recorded as ventilated that is lost to follow-up or dies before 28 days, will be censored at the date of last follow-up, or date of death. This outcome will be analysed as a time-to-event using the methodology described in 17.2.2.1 above.

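### The rule for patients discharged alive is missing for time-to-death and time-to-first ventilation; censoring them at discharge would inflate risks and distort the hazard ratio

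*SAP*

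**What the plan says.** **End of observation.** SAP 8.8: "All patients are followed up until discharge, death, or 28 days post baseline – whichever occurs first". SAP 8.9 stops data collection at the same point: "then on death, discharge or day 28 post hospitalisation, depending which is soonest". No status is scheduled to be collected after discharge.

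**Time-to-death (17.2.2.3).** Two sentences set the censoring time: "Any patient alive at the end of the study period will be censored at 28 days" and "Any patient lost to follow-up prior to 28 days will be censored at their last known follow-up". Neither names discharge. The section then takes its methodology from 17.2.2.1.

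**Time-to-first ventilation (17.2.2.6).** Unventilated patients who die or are lost before day 28 "will be censored at the date of last follow-up, or date of death". There is no counterpart to the day-28 sentence of 17.2.2.3, and the methodology again comes from 17.2.2.1.

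**Time-to-recovery (17.2.2.1), the section both import.** Its general rule is "All other patients are censored at last available follow-up or 28 days (whichever occurs first"). For the event that prevents recovery it has a special rule: "All deaths before 28 days (with no prior recovery) will be censored at day 28". It specifies a Cox model and Kaplan-Meier graphs, overall and by age group.

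**The concern.** Most patients in such a cohort should leave hospital alive before day 28, so the unstated rule covers a large share of the data. Two programmers working from this text could censor the same patient on day 7 or on day 28.

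The choice matters because discharge is not independent of prognosis. Patients sent home are those least likely to die or to need ventilation. Cox and Kaplan-Meier methods let those still in hospital stand in for them, so risk is overstated. If stay differs by treatment, the hazard ratio is distorted as well. A difference in stay is what the plan is looking for: section 6.2 reports faster recovery on remdesivir against placebo, and section 9.2 uses time-to-recovery as its stand-in for length of stay.

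The plan handles a competing event in 17.2.2.1 by holding deaths to day 28, but carries no equivalent rule to death or ventilation.

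**Working it through.** **1. The plan's own figure.** Section 17.2.1 projects deaths at day 14: 500 × 0.031 = 15.5, rounded to 16; doubled for 1:1 matching, 31 to 32. This reproduces, but it says nothing on length of stay or 28-day risk. The inputs below are therefore assumptions.

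**2. Assumptions.** Control survivors have exponential time to discharge with median 10 days, so λ₀ = ln 2 / 10 = 0.0693 per day. The discharge rate on remdesivir is r·λ₀, with r = 1.25 or 1.5. 28-day mortality m is 5%, 10% or 20%. Death times are 28 × Beta(1.3, 1.7), mean 12.1 days, with survival function S(t).

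**3. Equal deaths in both groups, censoring at discharge.** The fraction still in the risk set at day t is

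R(t) = m·S(t) + (1 − m)·exp(−λt).

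Deaths are the same in both groups, so the hazard ratio at t is R_control(t) / R_RDV(t). At t = 10, m = 0.10, r = 1.5, with S(10) = 0.578:

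- control: 0.1 × 0.578 + 0.9 × 0.500 = 0.508
- remdesivir: 0.1 × 0.578 + 0.9 × 0.354 = 0.376
- ratio: 0.508 / 0.376 = 1.35, where the truth is 1.00

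The ratio rises with t (1.16 at day 5, 1.53 at day 14). Cox models fitted to 400,000 simulated patients per group give the averaged value:

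| m | r | HR, censored at discharge | HR, held to day 28 |
|---|---|---|---|
| 5% | 1.25 | 1.22 | 0.99 |
| 5% | 1.5 | 1.47 | 0.99 |
| 10% | 1.25 | 1.22 | 1.01 |
| 10% | 1.5 | 1.46 | 1.00 |
| 20% | 1.25 | 1.19 | 1.00 |
| 20% | 1.5 | 1.40 | 1.00 |

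A separate simulation with the same assumed median stay and mortality range gave 1.18–1.25 at r = 1.25 and 1.32–1.39 at r = 1.5, against 0.99–1.07 when held to day 28.

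**4. False-positive rate.** With 500 remdesivir patients, m = 10%, two-sided 5% tests and 1,500 runs:

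| r | Matching | Censored at discharge | Held to day 28 |
|---|---|---|---|
| 1.25 | 1:1 | 16% | 5% |
| 1.25 | 1:4 | 21% | 4% |
| 1.5 | 1:1 | 48% | 5% |
| 1.5 | 1:4 | 62% | 5% |

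**5. Kaplan-Meier.** With density f(t) of death times, the estimate at day 28 tends to 1 − exp(−∫ m·f(t)/R(t) dt). At a true 10% this is 23% in controls and 36% on remdesivir with r = 1.5. The inflation in controls needs no treatment difference.

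**6. Equal in-hospital death hazard h instead.** True 28-day in-hospital mortality is h/(h + λ) × [1 − exp(−28(h + λ))]. With h = 0.008:

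- control: 0.008/0.0773 × (1 − e^−2.165) = 9.2%
- remdesivir, r = 1.5: 0.008/0.1120 × (1 − e^−3.135) = 6.8%

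Censoring at discharge returns an HR of 1.00. Holding to day 28 returns 0.74. Kaplan-Meier under discharge censoring reads 1 − exp(−28 × 0.008) = 20% in both groups.

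**7. Ventilation.** With 10% ventilated and 10% dying unventilated in both groups, censoring at discharge and death gives an HR of 1.10 (r = 1.25) and 1.22 (r = 1.5). Holding both to day 28 gives 0.99 and 1.00.

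**The case against.** The plan nowhere states that time-to-death is censored at discharge. Discharge is a planned end of follow-up, not a loss. Section 8.1 sets the time-scale to 28 days, and Appendix Table 1 scores discharged patients separately from those lost. A patient discharged alive can fairly be read as alive at the end of the study period, and then day-28 censoring already applies. This stands for time-to-death: the defect is text that points two ways, not a wrong rule. It does not help ventilation, which lacks that sentence and draws on daily in-hospital forms.

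A reader might infer that remdesivir would look harmful. The documents do not support that as a general claim. It needs discharge as the censoring time, faster discharge on remdesivir and equal 28-day mortality. With equal in-hospital hazards the error is a masked benefit.

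Censoring ventilation at death yields a legitimate cause-specific hazard ratio. It fails only if it, or 1 minus Kaplan-Meier, is read as the 28-day risk of ventilation. Replacing the ventilation outcomes with a composite would be a preference, not a correction. The special rule for deaths in time-to-recovery also has a stated reason: a footnote adopts the definition of the placebo-controlled trial the plan cites.

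The sizes rest on assumed stays and death times. That stands too: the plan gives no such figures.

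**Conclusion.** The concern holds as an unresolved censoring rule in two secondary outcomes. For time-to-first ventilation, the imported rule leads to censoring at discharge. For time-to-death, the two sentences contradict each other for a patient discharged alive.

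If discharge is the censoring time, the hazard ratio for death is about 1.2 to 1.4 (up to 1.47 in one set of runs) at discharge rate ratios of 1.25 to 1.5 and equal 28-day mortality. It is about 1, with a real benefit hidden, when in-hospital hazards are equal. Kaplan-Meier 28-day mortality is roughly doubled or more at a true level near 10%. These sizes assume a median stay of 10 days and 28-day mortality of 5–20%; the informativeness of the censoring does not depend on those exact values.

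It would be wrong to infer that the primary result is at risk. The 14-day and 28-day mortality analyses are binary logistic models, and this censoring rule does not affect them.

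**What to change.** **17.2.2.3.** State that patients discharged alive stay at risk and event-free and are censored at day 28, assumed alive unless a later death is recorded. Reserve early censoring for true loss to follow-up, for example a missing outcome form. Label the result in-hospital mortality to day 28.

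**17.2.2.6.** Hold patients discharged unventilated to day 28. Treat death without ventilation as a competing event, and present cumulative incidence in place of 1 minus Kaplan-Meier. The cause-specific hazard ratio may stay if it is labelled as such.

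**17.2.2.7 and 17.2.2.8.** Leave the outcomes as defined, and report death without ventilation beside them.

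**Cost.** A few sentences and a change in the censoring code, with no new data. Deaths and ventilation after discharge remain unseen, as they are now. Settling the rule before analysis also removes a choice that could otherwise be made with the results in view.

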#### 17.2.2.5. Length of time receiving supplementary oxygen

The DAILY CRF will be used to determine the number of days where oxygen was recorded as given. Missing daily CRFs will be imputed if and only if adjacent days are not missing, and as follows:

Day before	Day after	Impute for missing day
Oxygen	Oxygen	Oxygen
No oxygen	No oxygen	No oxygen
Oxygen	No oxygen	0.5 days on oxygen
No oxygen	Oxygen	0.5 days on oxygen

The outcome will be the total number of days either known or imputed to be on oxygen. Days where no imputation is possible will be excluded from the analysis, under the assumption that missingness is equally likely regardless of treatment. An assessment of the proportion of missing daily CRFs per patient will be made for each treatment group to check this assumption: an arbitrary margin of acceptability of an absolute difference of 10% will indicate the assumption holds. If the assumption holds, ‘Days on oxygen’ will be modelled using linear regression, with treatment group fitted as a covariate, and adjusting for the key confounders: age, sex, and number of comorbidities at baseline. The mean (SD) days will be presented for each treatment group, and the difference in days comparing RDV with controls, estimated from the model, will be presented together with a 95% CI.

If the assumption does not hold, modelling will not be used, and only descriptive statistics will be presented.

#### 17.2.2.6. Time-to-first ventilation

The DAILY CRF will be used to define, where possible, date of first use of ventilation. Any patient not recorded as ventilated that is lost to follow-up or dies before 28 days, will be censored at the date of last follow-up, or date of death. This outcome will be analysed as a time-to-event using the methodology described in 17.2.2.1 above.

#### 17.2.2.7. Use of non-invasive ventilation at any time during 28 days post baseline

The total number of patients requiring any non-invasive ventilation during the 28 days post baseline will be presented. The effect of RDV on the risk of requiring non-invasive ventilation will be evaluated using the same methodology as used in 17.2.1 above.

#### 17.2.2.8. Use of mechanical ventilation / ECMO at any time during 28 days post baseline

The total number of patients requiring any mechanical ventilation/ECMO during the 28 days post baseline will be presented. The effect of RDV on the risk of requiring mechanical ventilation/ECMO will be evaluated using the same methodology as used in 17.2.1 above.

#### 17.2.2.9. Acute renal injury/acute renal failure at any time during 28 days post baseline

The total number of patients experiencing either acute renal injury or acute renal failure during the 28 days post baseline will be presented. The effect of RDV on the risk of this complication will be evaluated using the same methodology as used in 17.2.1 above.

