### 8.3. Baseline: definition

We take a common baseline to be ‘date of hospitalisation due to COVID’. It is important to note that this is not necessarily when RDV was initiated, though it is likely that it was administered soon after admission. The definition of baseline depends on the where the infection was acquired:

Community acquired COVID-19 i.e. admitted with symptoms consistent with COVID-19:

Baseline = Date of admission to hospital

For hospital acquired COVID-19 :

Baseline = Date positive COVID-19 test was collected

‘Hospital acquired’ is defined as: symptom onset at least 5 days after hospital admission.

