##### 8.4.2. Exclusion criteria

- Requiring a high flow cannula, any ventilation or ECMO during first 24 hours post baselinec
- Pregnant
- Chronic kidney disease
- RDV initiated  $> 24$  hours post baselined
- Is a COVID-19 re-admission (was previously hospitalised for COVID-19)
- Missing Day 1 Daily Treatment CRF
- Missing ‘Medication’ section of the Outcome CRF

---

a RDV was recommended in people aged 12 and over, and weighing over 40kg. Weight was not generally measured at baseline for practical reasons, so we have excluded children aged 12-17 in order to be sure that no-one in the control group was likely to weigh less than 40kg.

b This criteria is an ideal, to measure the effectiveness of RDV initiated close to baseline. If RDV is more routinely given later than this, we will either remove this criteria, or move the window of inclusion to say 3 days. Statistics describing when RDV treatment was initiated compared with baseline, will be presented.

c This subgroup will be analysed separately (see Section 19).

d See footnote b above.

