### 8.7. Definition of treatment groups

The analysis cohort will be split into two treatment groups: RDV and non-RDV. As the study is observational, allocation of treatment is decided by clinicians.

A matching process will be carried out to link RDV patients with non-RDV patients as follows:

A logistic regression with dependent variable RDV (Yes/No) will be fitted including the following covariates:

1. Month of baseline
2. Tier of participating centre (0 / 1 and 2)
3. Sex
4. Age
5. Broad ethnicity group (White / Asian / Black / Other)
6. Clinically extremely vulnerable status (Yes: Cancer / Yes: Severe respiratory condition / Yes: on immunosuppression therapy / Yes: Other / No)
7. Comorbidities: Diabetes (Y/N), Hypertension (Y/N), Obesity (Y/N), Chronic Cardiac disease (Y/N), CPD (Y/N), Asthma (Y/N)
8. Where COVID was acquired (Community / Hospital)
9. Admitted to HDU/ICU at baseline (Y/N)

Note: a pragmatic approach will be taken – the list above defines a best-case set of matching criteria; it may be necessary for categories to be collapsed to simplified discriminators (e.g. White vs Other ethnicity, or ‘Total number of comorbidities’), should the model become over-parametrised. If possible, 2nd order interactions will be investigated, and if statistically significant, added to the model. All main effects will be retained in the model, even if not significant.

The fitted model will be used to calculate the probability of receiving RDV for each patient according to their baseline factors. The probability calculated is called their propensity score (PS). Boxplots will

be presented showing the distribution of PS in each treatment group. Patients who were given RDV will then be matched to a control patient / patients with a similar PS who did not get RDV, using a nearest neighbour matching algorithm and a pre-specified maximum difference in PS (calliper width) of 0.2 standard deviations. The ratio of RDV patients to controls may be 1:1 or higher – to a maximum of 1:4 (Rassen (2012) suggests that 1:n matching leads to higher precision in estimating effect sizes, with a cost of a small increase in bias with increasing n). Controls are chosen without replacement, so may not be matched to more than one RDV patient.

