#### 17.2.2.10. Liver dysfunction at any time during 28 days post baseline

The total number of patients experiencing any liver dysfunction during the 28 days post baseline will be presented. The effect of RDV on the risk of this complication will be evaluated using the same methodology as used in 17.2.1 above.

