## 20. Safety

The number and percentage of patients experiencing specific complications at any time during the 28 days post baseline, will be reported for both groups. Complications to be summarised are those appearing on the Outcome CRF.

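### The renal and liver outcomes do not require new onset, so conditions present at baseline or arising before remdesivir starts are counted as outcomes and modelled as drug effects

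*SAP*

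**What the plan says.** SAP Section 17.2.2.9 defines the renal outcome: "The total number of patients experiencing either acute renal injury or acute renal failure during the 28 days post baseline will be presented". Section 17.2.2.10 follows the same pattern: "The total number of patients experiencing any liver dysfunction during the 28 days post baseline will be presented". Both are then analysed by the logistic regression of Section 17.2.1, giving an odds ratio for RDV against controls, with age, sex and comorbidity count as the intended adjustment. Section 20 tabulates complications over the same window and names its source: "Complications to be summarised are those appearing on the Outcome CRF".

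Baseline (Section 8.3) is the admission date for community-acquired infection and the date of the positive test for hospital-acquired infection. The SAP warns that "this is not necessarily when RDV was initiated". RDV must start within 24 hours of baseline, but footnote b to Section 8.4 adds that if RDV is routinely given later, "we will either remove this criteria, or move the window of inclusion to say 3 days". The only organ-related exclusion is "Chronic kidney disease". Section 8.7 states that "allocation of treatment is decided by clinicians".

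**The concern.** An outcome meant to show an effect of RDV should count events that could follow RDV. As written, a patient who arrives with acute renal injury or deranged liver function, or develops it between baseline and the start of RDV, can be counted. No later step catches this:

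- The propensity model (8.7) has no specific renal or hepatic covariate.
- The balance check (8.7) uses a mortality risk score built on sex, age and comorbidity count.
- The outcome model uses the same three factors.
- The baseline table (17.1) does not list acute renal or liver status, so a reader could not see an imbalance.

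For ventilation the SAP does take the necessary step. Patients on high-flow cannula, ventilation or ECMO in the first 24 hours are excluded (8.4.2), and ventilated patients are analysed separately (19). The ventilation outcomes therefore start from patients free of the event; the renal and liver outcomes do not.

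The work was commissioned to address safety as well as efficacy (6.1). These are the only two organ complications given a modelled comparison; Section 20 only tabulates the rest. An odds ratio near 1 could be taken as reassurance.

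**Working it through.** **The plan's own figures.** The SAP gives no expected rate for renal injury or liver dysfunction. Its only projected event count is for deaths (17.2.1): 500 × 0.031 = 15.5, rounded to 16, and doubled to 32 under 1:1 matching. That reproduces but says nothing about these outcomes. All rates below are therefore assumptions.

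**Formula.** Let p be the proportion with the condition already present and r the risk of a new event in those free of it. The proportion counted under the SAP wording is p + (1 − p) × r. The odds ratio compares this quantity between groups.

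**Assumed new-event risks:** RDV 10%, controls 8%. Odds ratio for new events = (0.10/0.90)/(0.08/0.92) = 1.28.

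| Already present, RDV v control | Counted on RDV | Counted in controls | Odds ratio |
|---|---|---|---|
| 0% v 0% | 0.100 | 0.080 | 1.28 |
| 3% v 3% | 0.03 + 0.97×0.10 = 0.127 | 0.03 + 0.97×0.08 = 0.108 | 1.21 |
| 10% v 10% | 0.10 + 0.90×0.10 = 0.190 | 0.10 + 0.90×0.08 = 0.172 | 1.13 |
| 8% v 10% | 0.08 + 0.92×0.10 = 0.172 | 0.172 | 1.00 |
| 5% v 10% | 0.05 + 0.95×0.10 = 0.145 | 0.172 | 0.82 |
| 3% v 10% | 0.127 | 0.172 | 0.70 |
| 10% v 5% | 0.190 | 0.05 + 0.95×0.08 = 0.126 | 1.63 |

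The equal-prevalence rows need no assumption about prescribing. The risk difference shrinks by the factor 1 − p (from 0.020 to 0.018 at 10%) while the background risk rises, so the odds ratio moves towards 1. The unequal rows are hypothetical. The last one shows that imbalance the other way exaggerates harm.

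**A larger assumed effect.** With control risk 5% and RDV risk 10% (odds ratio 2.11), 500 per group and two-sided 5% testing, power is about 85%. Equal prevalence of 5% gives 14.5% v 9.75%, odds ratio 1.57, power about 63%. Equal prevalence of 10% gives 19.0% v 14.5%, odds ratio 1.38, power about 48%. With 5% on RDV against 10% in controls, both groups show 14.5% and the odds ratio is 1.00.

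**Where reversal fails.** With control risk 10% and RDV risk 20% (odds ratio 2.25), even 2% v 10% already present leaves an odds ratio of 1.17. A large harm is weakened there, not reversed.

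**The case against.** The strongest reply is that the wording already implies new onset: patients experience a complication after baseline, and pre-existing conditions are handled separately as comorbidities. That reading is possible, but no rule makes it operative, and analysts could code it differently. It also fits poorly with hospital-acquired infection, where symptoms begin at least 5 days after admission and baseline is the test date. A complication of that hospital stay can therefore predate baseline.

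Second, the pre-RDV window is at most 24 hours as planned. That limits events arising between baseline and RDV unless footnote b is used, but does nothing about conditions already present at baseline.

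Third, Section 11 concedes that observational data limit the inference. That covers residual confounding, but not an outcome definition that can be tightened.

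A reader might infer more: that clinicians withheld RDV from patients with acute renal or liver injury, so prevalent cases collected in the control group and RDV will look protective. The SAP does not support this. It says only that clinicians choose treatment. The chronic kidney disease exclusion, among criteria meant to build an RDV-eligible cohort, is indirect support for the kidney only; for the liver there is none. Any gap would also have to survive matching on age, comorbidities, place of acquisition, HDU/ICU admission and month.

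Nor can it be claimed that the forms are unable to separate new from existing events. The complication item is not shown, and only Section 20, not 17.2.2.9 or 17.2.2.10, names the Outcome CRF.

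**Conclusion.** The point holds as a defect in the definition of two secondary outcomes. Followed as written, Sections 17.2.2.9 and 17.2.2.10 can count events that predate RDV and report them as its effect. Provided some patients have the condition at baseline, dilution follows even with balanced groups: under the assumed 10% v 8%, from 1.28 to 1.21 at 3% prevalence and to 1.13 at 10%. Cancellation or reversal (0.82 at 5% v 10%, 0.70 at 3% v 10%) needs an excess in controls that the SAP does not state; it is a possibility, not a prediction. The actual size cannot be derived from the SAP. The primary outcome is not affected. The change should be made before analysis.

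**What to change.** For outcomes 9 and 10 only:

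1. Exclude from each analysis, in both groups, patients with that condition recorded at admission or on day 1, and count only events first recorded after day 1.
2. If footnote b widens the RDV window, count from the end of that window in both groups. If the limit is removed altogether no such day exists; fix and document a common starting day, or give descriptive results only. Do not restart follow-up match by match, which would not fit the pooled analysis in footnote f.
3. Re-check balance in the reduced sets, since removing patients after matching can disturb it.
4. Add baseline renal and liver status to the table in 17.1. Where further detail is recorded, adjust for it in these two models, within the SAP's guide of 10 events per covariate. Keep it out of the main propensity score: scores need complete covariates (Section 18), so adding it there could shrink the cohort for the primary analysis.
5. If the forms cannot separate new from existing events, present counts by group and do not interpret an odds ratio as an RDV effect.

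The cost is SAP wording, use of admission and day-1 data, fewer patients in two secondary models, and loss of early events and of any worsening in patients who already had the condition. The primary analysis does not change.
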